4.5. Randomization and blinding

Eligible participants will be randomized into one of 4 treatment arms in equal proportions:

- Active Multivitamin and Active Cocoa Extract;
- Active Multivitamin and Placebo Cocoa Extract;
- Placebo Multivitamin and Active Cocoa Extract;
- Placebo Multivitamin and Placebo Cocoa Extract.

The algorithm will use a randomized permuted block approach, stratified by (at minimum) sex, age group, and recruitment center (WHI or BWH). The date of randomized treatment assignment will be considered the formal enrollment date.

Whenever possible, household partners (e.g., spouse/partner) of a randomized COSMOS participant will be assigned to the same treatment group, as the corresponding randomized participant. To ensure balance within strata at the participant-level, the household partner will occupy the next available allocation with the same treatment, as the randomized participant. The strata of the household partner will be determined by the household partner's individual characteristics, and not the characteristics of the corresponding randomized participant.

BWH will receive all calendar packs for distribution to COSMOS participants and maintain blinding to treatment assignments.

5.0. Outcomes

Primary and secondary outcomes will be ascertained initially through self-report, proxy-report, or death certificate, and confirmed through medical record review using definitions and procedures established in the WHI. For COSMOS participants recruited from WHI, all cancer events and ~25% of CVD events in WHI will be adjudicated through currently funded ongoing WHI procedures. The remaining CVD events among WHI participants and all cancer and CVD events in the remaining participants will be documented and adjudicated using identical definitions and procedures by WHI physician adjudicators and COSMOS staff at BWH who are blinded to randomization assignment.

5.1. Primary Outcomes

Cocoa Extract: Centrally adjudicated major cardiovascular events, including myocardial infarction, stroke, cardiovascular mortality, coronary revascularization, unstable angina or ACS requiring hospitalization, carotid artery surgery, and peripheral artery surgery or angioplasty;

Multivitamin: Invasive cancers of any site other than non-melanoma skin cancer as confirmed by medical record review and coded according to SEER standards.

5.2. Secondary Outcomes

Cocoa Extract: Composite endpoint of MI, stroke, cardiovascular mortality, and coronary revascularization; invasive cancers of any site other than non-melanoma skin cancer as confirmed by medical record review and coded according to SEER standards.

Multivitamin: Centrally adjudicated major cardiovascular events, including myocardial infarction, stroke, cardiovascular mortality, coronary revascularization, unstable angina or ACS requiring hospitalization, carotid artery surgery, and peripheral artery surgery or angioplasty.

Cocoa extract and a daily multivitamin:

Major cardiovascular events (the combined endpoint of composite endpoint of MI, stroke, cardiovascular mortality, coronary revascularization, unstable angina or ACS requiring hospitalization, carotid artery surgery, and peripheral artery surgery or angioplasty) plus all-cause mortality;

Individual cardiovascular events, including MI, stroke, cardiovascular mortality, coronary revascularization, unstable angina or ACS requiring hospitalization, carotid artery surgery, peripheral artery surgery or angioplasty, and total mortality; plus site-specific cancers, including breast, colorectal, and lung cancer;

Invasive cancer in participants with a history of cancer at COSMOS baseline.

5.3. Tertiary Outcomes

Cocoa extract and/or a daily multivitamin: Synergistic effects on risk of major cardiovascular events or cancer, and if the effects vary by nutritional status or medication use.

5.4. Ancillary Outcomes

COSMOS Mind – Cocoa extract and/or a daily multivitamin: Telephone-based assessments of global cognitive function, executive function, and memory.

COSMOS Web – Cocoa extract: Internet-based neuropsychological testing battery, including the ModBent test (cognitive test of novel object recognition), the Spatial Learning Task, and the Flanker Task (cognitive test of attention, inhibition, and executive control).

COSMOS Eye – Cocoa extract and/or a daily multivitamin: cataracts, cataract surgery, and age-related macular degeneration (AMD).

COSMOS Falls and Physical Performance – Cocoa extract and/or a daily multivitamin: Injurious fall(s) resulting in healthcare utilization (visit to a healthcare provider or hospital); recurrent falls; physical performance as assessed by grip strength (by dynamometer), walking speed (6 meters); and the Short Physical Performance Battery including tests of standing balance, walking speed, and chair stands; incident total, spine, forearm/wrist, and hip fractures; and bone density changes.

COSMOS Inflammaging and Epigenetic Aging – Cocoa extract and/or a daily multivitamin: epigenetic aging; inflammaging; and effects on inflammaging are mediated by epigenetic aging, and the impact on CVD risk.

6.0. Sample size and power

Power calculations for the primary endpoints of major cardiovascular events and total invasive cancer are based upon a 2x2 factorial trial in approximately 22,000 participants, including 13,000 women aged ≥ 65 years and 9,000 men aged ≥ 60 years. Based on the log-rank test (equivalent to score tests for hazard ratios from a Cox model without covariates), Freedman³⁶ has shown that the power, $1-\beta$, of this test to detect a specified hazard ratio HR based on a two-sided test with significance level α is a simple function of the number of accrued events, m , in the two groups combined: $1-\beta = \Phi(\sqrt{m}(|HR-1|)/(|HR+1|) - Z_{1-\alpha/2})$, where Φ is the standard normal cumulative distribution function. The factorial design of this trial is motivated primarily by efficiency. The scientific justification for testing each intervention is independent of the other and stands alone. Therefore each comparison (multivitamins versus placebo and cocoa extract versus placebo) will be based on a marginal test (but controlling for the other intervention) at a level of $\alpha = 0.05$.

Estimates of study power and the expected numbers of confirmed, accrued events in Table 1 are based on the following assumptions: (1) independent and equal allocation of participants to each treatment; (2) an age distribution based on that observed among WHI women ≥ 65 years and men aged ≥ 60 years responding to the VITAL mailings; (3) annualized age-specific event rates based on observed rates during WHI and VITAL follow-up, adjusted for aging; (4) same event rates for men and women given that women are approximately 5 years older than men; (5) mean trial follow-up of 4 years, with nominal loss to follow-up as seen previously in WHI, VITAL, and mail-based trials by the BWH Division of Preventive Medicine; and (6) an average of 80% compliance. These assumptions remain the same as proposed for our original power calculations for 18,000 participants.

With approximately 22,000 randomized participants, there will be at least 80% power to detect a 11% relative hazard reduction in total CVD, and $>95\%$ power to detect such a reduction in the important composite of total CVD plus all-cause mortality with the expected number of events. Similarly, there would be at least 90% power to detect a 14% reduction in total cancer. Power for key secondary outcomes are highly dependent on the frequency of the events.

Table 1. Power for effects of a single agent on specified endpoints in a factorial trial of 22,000 women and men, with 4 years of treatment and follow-up (#s in parentheses are expected number of events in both groups combined)

Observed RR *	True RR †	Total CVD	Total CVD + Mortality	Total Cancer	CVD death	Stroke	MI	Breast cancer
Placebo event rate (per 100 p-y)		3.0	5.0	2.2	1.0	0.9	0.8	0.8
0.90	0.875	76% (2479)	93% (4106)	63% (1837)	- (824)	- (743)	- (661)	- (661)
0.85	0.812	98% (2416)	>99% (4005)	93% (1790)	64% (803)	59% (723)	54% (644)	54% (644)
0.80	0.750	>99% (2353)	>99% (3903)	>99% (1743)	88% (781)	84% (704)	80% (627)	80% (627)
0.75	0.687	>99% (2290)	>99% (3801)	>99% (1695)	98% (760)	96% (685)	94% (609)	94% (609)
0.70	0.625	>99% (2226)	>99% (3697)	>99% (1648)	>99% (738)	>99% (665)	99% (592)	99% (592)
0.65	0.560	>99% (2162)	>99% (3592)	>99% (1600)	>99% (717)	>99% (646)	>99% (575)	>99% (575)

* Observed RR = intent-to-treat RR, including noncompliant participants and 80% compliance.

† True RR = that with perfect compliance.

- Power < 50%

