Cox proportional hazards models estimated HRs using an indicator variable for cocoa extract treatment and stratifying the baseline hazard functions by sex, age group, recruitment source, and multivitamin intervention arm. COSMOS was designed for 22,000 participants with $\geq 80\%$ power to detect a 11% relative hazard reduction in total CVD, and $>95\%$ power to detect the same reduction for the secondary outcome of CVD plus all-cause mortality. We also had $\geq 90\%$ power to detect a 14% reduction in total cancer. Models were constructed for each clinical outcome, where person-time for each outcome was counted as days from randomization to the first post-randomization diagnosis of the designated outcome. Follow-up was censored at date of last contact, death, or end of the trial on December 31, 2020, whichever came first.

Kaplan-Meier cumulative incidence curves, cumulative HRs, interactions between randomization groups with trial-time, and analyses that excluded the first 1 and 2 years of follow-up assessed whether treatment effects varied over time (4). Nine subgroup analyses examined effect modification by *a priori* (concurrent multivitamin randomization assignment, sex, age, and use of statins or aspirin) and *post hoc* (history of CVD, smoking status, number of CVD risk factors, and chocolate consumption) factors. Secondary outcomes (n=14) mostly constituted subtypes of CVD or cancer. Statistical significance ($P \leq 0.05$) was assessed with two-sided p-values. We did not adjust P-values or confidence intervals for multiple testing. Consequently, results for secondary outcomes, other outcomes, subgroup analyses, and other analyses should be interpreted cautiously and considered hypothesis generating. At the nominal 0.05 level, we would expect less than one interaction and one secondary outcome to be significant by chance alone.

Per-protocol analyses censored follow-up when the participant discontinued trial pills, began outside non-study use of a cocoa supplement, and/or took <75% of study pills. HRs and 95% CIs were estimated using Cox regression models, weighted by the inverse probability of dependent-censoring for non-compliance (5). Additional analyses compared self-reports of non-monitored outcomes or potential side effects by intervention group. Analyses were performed using SAS 9.4.

Multivitamin-specific data analyses

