Baseline characteristics by treatment groups were compared using chi-squared tests of association, a t-test contrasted age at randomization, and Wilcoxon rank-sum tests compared non-normally distributed variables such as body mass index and exercise. Statistical significance ($P \leq 0.05$) was assessed with two-sided p-values. Our primary analyses were based on the intention-to-treat principle for time-to first event data.(1) Cox proportional hazards models estimated HRs using an indicator variable for MVM assignment and stratifying the

baseline hazard functions by sex, age group, recruitment source, and cocoa extract intervention arm. The trial was designed for 22,000 participants with $\geq 90\%$ power to detect a 14% relative hazard reduction in total cancer. Models were constructed for each clinical outcome, where person-time for each outcome was counted as days from randomization to the first post-randomization diagnosis of the designated outcome. Follow-up was censored at date of last contact, death, or end of the trial on December 31, 2020, whichever came first.

Kaplan-Meier cumulative incidence curves, cumulative HRs, interactions between randomization groups with trial-time, and analyses that excluded the first 2 years (for cancer endpoints) or 1 year (for CVD endpoints) of follow-up assessed whether treatment effects varied over time.(4) Ten subgroup analyses examined effect modification by *a priori* (concurrent cocoa extract randomization assignment, sex, age, history of cancer, use of statins or aspirin) and *post hoc* (smoking status, fruit and vegetable intake at baseline, use of dietary supplements or multivitamins prior to randomization) factors. We did not adjust P-values or confidence intervals for multiple testing. Secondary outcomes mostly constituted subtypes of cancer or CVD, and numbered fewer than twenty. Results for secondary and exploratory outcomes and those for subgroup analyses should therefore be interpreted with caution and considered hypothesis generating. At the nominal 0.05 level, we would expect less than one interaction and one secondary outcome to be significant by chance alone.

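### The power stated as at least 90% for a 14% reduction in total cancer is 89.1% to 89.7% on Table 1's own events, so the lower bound is narrowly missed

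*Protocol*

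**What the plan says.** Protocol section 6.0 uses Freedman's log-rank formula, in which power "is a simple function of the number of accrued events" in the two groups together, with a two-sided test at 0.05 for each marginal comparison. The caption of Table 1 identifies the figures in parentheses as the "expected number of events in both groups combined". For total cancer these are 1,837 at an observed relative risk (RR) of 0.90 (power 63%) and 1,790 at 0.85 (power 93%). There is no row for 0.86. The footnote defines the scale: "Observed RR = intent-to-treat RR, including noncompliant participants and 80% compliance".

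The text of section 6.0 then states that "there would be at least 90% power to detect a 14% reduction in total cancer". The SAP carries the figure over as 90% or more twice: under the cocoa extract analyses ("power to detect a 14% reduction in total cancer") and under the multivitamin analyses ("power to detect a 14% relative hazard reduction in total cancer").

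**The concern.** The claim is worded as a lower bound, and it concerns one of the two primary endpoints. The formula, the alpha level and the event counts are all printed, so a reader can check it. On those inputs the answer comes out below 90%. What is at stake is the accuracy of a stated figure that appears in three places, not the adequacy of the trial.

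**Working it through.** **Inputs (protocol section 6.0 and Table 1).** Two-sided alpha 0.05, z = 1.960. Power = Φ(√m × (1 − HR)/(1 + HR) − 1.960), with m the events in both groups. Cancer events: 1,790 at RR 0.85 and 1,837 at RR 0.90. The 14% is read as an observed (intent-to-treat) RR of 0.86, taken as the HR; the SAP's multivitamin section puts it on the hazard scale.

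**Step 1. Reproduce the companion statements at HR 0.89.**
- Total CVD: m = 2,416 + 0.8 × (2,479 − 2,416) = 2,466.4. Power = Φ(49.66 × 0.11/1.89 − 1.960) = Φ(0.930) = 82.4%. Stated: at least 80%. Holds.
- CVD plus mortality: m = 4,005 + 0.8 × (4,106 − 4,005) = 4,085.8. Power = Φ(63.92 × 0.11/1.89 − 1.960) = Φ(1.760) = 96.1%. Stated: above 95%. Holds.

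**Step 2. Cancer at HR 0.86 by the stated formula.**
- m = 1,790 + 0.2 × (1,837 − 1,790) = 1,799.4.
- Power = Φ(42.42 × 0.14/1.86 − 1.960) = Φ(1.233) = **89.1%**.

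**Step 3. Does the interpolation matter?** At HR 0.86 the formula gives 89.0% with m = 1,790 and 89.7% with m = 1,837, the largest cancer count in the table. No printed cancer count reaches 90%.

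**Step 4. What 90% would need.** m = (3.2415 × 1.86/0.14)² = 1,854.7, which is 55 events (3.1%) more than 1,799.4. With Table 1's events, the formula reaches 90% at HR 0.8579, about a 14.2% reduction.

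**Step 5. Other two-sided methods.** The documents do not say how the power cells were computed. Two constructions fit them better than putting RR directly into the formula. Both assume annual compounding over 4 years with 11,000 per group, and a cancer rate of 2.27 per 100, the value that reproduces the printed cancer counts. This is an inference from the numbers.
- *Two proportions.* Placebo risk 1 − (1 − 0.0227)⁴ = 0.0878; active risk 1 − (1 − 0.86 × 0.0227)⁴ = 0.0758. Power **89.7%**; 90% is reached at about a 14.1% reduction.
- *RR treated as an annual-risk ratio and converted to an HR.* HR = ln(1 − 0.86 × 0.0227)/ln(1 − 0.0227) = 0.8586. The stated formula on 1,799.4 events gives **89.7%**.

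Table 1 has 15 distinct numeric power cells (breast cancer duplicates MI). Both constructions round to print in all 15. The formula with HR set equal to RR does so in 9 and is low in the other 6; the largest gap is 74.6% against 76% for CVD at 0.90.

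Further checks:

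| Method, cancer at 0.86 | Events | Power |
|---|---|---|
| Schoenfeld, HR 0.86 | 1,799 | 89.2% |
| Schoenfeld, HR 0.8586 | 1,799 | 89.85% |
| Stated formula, person-years at 2.2 per 100: 44,000 × 0.022 × 1.86 | 1,800 | 89.1% |
| Stated formula, 2.2 compounded | 1,746 | 88.2% |

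The second row is the most favourable calculation on Table 1's events. It still falls short, and it fits the table less well: it gives 93.51% for cancer at 0.85, where 93% is printed. A compounded rate of 2.3 with the converted HR would give 90.1%, but it implies about 1,822 events, more than Table 1 carries.

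**The case against.** The best defence is that this is rounding. The miss is under one point, 14.1% and 14.2% both round to the printed 14%, and the protocol speaks of approximately 22,000 participants. The constructions that match Table 1 best give 89.7%, which itself rounds to 90%. All of that stands, and it would fully support a statement of about 90%. It does not support a lower bound, which is what the protocol and both SAP sections state. The defence also rightly weighs against correcting the text to a flat 89%, since that rests on the calculation that fits the table's powers less well.

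It is also true that nothing now turns on the figure. The SAP is dated February 4, 2022 and follow-up ended on December 31, 2020, so no design decision depends on it.

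A reader might go further and infer that Table 1's placebo rate row is wrong, because annual compounding matches every count only with 3.1, 5.3 and 2.27 where 3.0, 5.0 and 2.2 are printed. The documents do not support that. They never state how the counts were derived, so compounding is a guess. The protocol assumes a mean follow-up of 4 years "with nominal loss to follow-up as seen previously in WHI", with no figure. If that loss is taken as 1.5% (an assumption), person-years at 3.02, 5.00 and 2.23 reproduce the three columns to within half a percent, and all three rates round to the printed values.

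**Conclusion.** The bound is not met as written. Power for a 14% reduction in total cancer is 89.1% by the stated formula and 89.7% by the constructions that best reproduce Table 1, a shortfall of 0.3 to 0.9 point. No two-sided method tried on Table 1's events reaches 90%. The result rests on the printed event counts, two-sided alpha of 0.05, and the 14% being an intent-to-treat effect.

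That last reading favours the plan. If the 14% were the perfect-compliance effect, the observed RR would be 1 − 0.8 × 0.14 = 0.888, with m about 1,826 and power about 72%. A reader might infer so large a gap, but the SAP's wording and the agreement of the CVD statements with the observed scale point the other way.

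Nor do the documents support inferring that the trial is too small for its cancer endpoint. The discrepancy is minor and does not touch the sample size, the test or the analysis.

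**What to change.** In protocol section 6.0, and in the SAP's cocoa extract and multivitamin sections, replace the lower bound of 90% with about 90% (89–90%). Alternatively, keep 90% and attach it to a reduction of about 14.2%. Use the same wording in all three places. The CVD and CVD-plus-mortality statements need no change. The cost is one restated figure in three places and a marginally less favourable power claim.

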2.0. Study Objectives

COSMOS is a randomized, double-blind, placebo-controlled, 2x2 factorial trial of a cocoa extract and a multivitamin supplement in up to 22,000 subjects (13,000 women and 9,000 men), including women recruited from active, older WHI participants and men and women who expressed interest in research being conducted by BWH. The primary objectives of this trial are to evaluate these agents for the maintenance of health. The specific hypotheses guiding the design of the trial are as follows:

2.1. Primary Hypotheses:

- 1) Cocoa extract (2 capsules/day containing a total of 600 mg/d flavanols, including 80 mg (-)-epicatechin, and 50 mg theobromine) (please see section 4.4 Intervention) will reduce the risk of major cardiovascular events, defined for these purposes as a composite endpoint of MI, stroke, cardiovascular mortality, coronary revascularization, unstable angina or acute coronary syndrome (ACS) requiring hospitalization, carotid artery surgery, and peripheral artery surgery or angioplasty;
- 2) A daily multivitamin will reduce the risk of invasive cancer (excluding non-melanoma skin cancer).

2.2. Secondary Hypotheses:

- 1) Cocoa extract will reduce the risk of a composite endpoint of MI, stroke, cardiovascular mortality, and coronary revascularization;
- 2) Cocoa extract will reduce the risk of invasive cancer (excluding non-melanoma skin cancer);
- 3) A daily multivitamin will reduce the risk of major cardiovascular events;
- 4) Cocoa extract and/or a daily multivitamin will reduce the combined endpoint of major cardiovascular events plus all-cause mortality;
- 5) Cocoa extract and/or a daily multivitamin will reduce the risk of individual cardiovascular events, including MI, stroke, cardiovascular mortality, coronary revascularization, unstable angina or ACS requiring hospitalization, carotid artery surgery, and peripheral artery surgery or angioplasty, and total mortality; plus site-specific cancers, including breast, colorectal, and lung cancer;
- 6) A daily multivitamin will reduce the risk of cancer among women and men with a history of cancer at baseline;

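### The breast-cancer column of Table 1 counts the 9,000 men, so expected events are about 69% too high and power is overstated by up to about 22 points

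*Protocol*

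**What the plan says.** Protocol section 6.0 bases its power calculations on "approximately 22,000 participants, including 13,000 women aged ≥ 65 years and 9,000 men aged ≥ 60 years". Its numbered assumptions include "independent and equal allocation of participants to each treatment", "same event rates for men and women given that women are approximately 5 years older than men" and "mean trial follow-up of 4 years, with nominal loss to follow-up". Power comes from the Freedman log-rank formula, which depends only on the hazard ratio, the two-sided alpha of 0.05 and the total number of events in the two groups combined.

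Table 1, titled "Power for effects of a single agent on specified endpoints in a factorial trial of 22,000 women and men", gives MI and breast cancer the same placebo rate, 0.8 per 100 person-years. The breast-cancer column has no women-only label, footnote or separate sample size. The equal-rates assumption makes no exception for it.

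Breast cancer is a named secondary outcome for both agents. Secondary hypothesis 5 in section 2.2 covers individual cardiovascular events "plus site-specific cancers, including breast, colorectal, and lung cancer", and section 5.2 repeats the list.

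**The concern.** The breast-cancer and MI columns agree in all six rows, in events and in power. MI occurs in both sexes and can draw on the whole trial, whereas breast cancer in effect draws on women alone. Two endpoints with the same rate can have the same expected counts only if they share the same person-years, so the match suggests that the men were included in the breast-cancer denominator.

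Breast cancer is the only site-specific cancer given a power column. A reader would conclude that the trial has 80% power for a 20% reduction. If the true figure is much lower, a null breast-cancer result could be given more weight as evidence of no effect than the design supports.

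**Working it through.** **Inputs (Protocol section 6.0 and Table 1).** N = 22,000, of whom 13,000 are women and 9,000 men; equal allocation; mean follow-up 4 years; placebo rate 0.008 per person-year; two-sided alpha 0.05, so z = 1.96. RR is the table's observed (intention-to-treat) RR.

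**Step 1: reproduce the printed counts.** With N/2 per group, two versions were run:

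- Flat person-years: m = (N/2) × 4 × 0.008 × (1 + RR)
- Exponential event times: m = (N/2) × [(1 − e^(−0.032)) + (1 − e^(−0.032·RR))]

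| Observed RR | Printed | Flat, N = 22,000 | Exponential, N = 22,000 | Exponential, N = 13,000 |
|---|---|---|---|---|
| 0.90 | 661 | 669 | 659 | 389 |
| 0.85 | 644 | 651 | 642 | 379 |
| 0.80 | 627 | 634 | 624 | 369 |
| 0.75 | 609 | 616 | 607 | 359 |
| 0.70 | 592 | 598 | 590 | 349 |
| 0.65 | 575 | 581 | 573 | 339 |

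The printed counts lie within about 1.2% of both calculations for 22,000 people and are far from those for 13,000.

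**Step 2: reproduce the printed power.** The protocol's formula is power = Φ(√m × |RR − 1|/(RR + 1) − 1.96). At RR 0.80 with m = 627: √627 = 25.04; 0.20/1.80 = 0.1111; 25.04 × 0.1111 − 1.96 = 0.82; Φ = 79.5%, printed as 80%. The other rows also reproduce (53.9%, 94.1%, 99.0%, 99.9%; 27% at RR 0.90, which the table shows as a dash).

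**Step 3: women only.** Multiply the printed events by 13/22 and use the same formula. At RR 0.80: 627 × 13/22 = 370.5; √370.5 = 19.25; 19.25 × 0.1111 − 1.96 = 0.18; Φ = 57.1%.

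| Observed RR | Printed events | Printed power | Women-only events | Women-only power | Loss, unrounded (points) |
|---|---|---|---|---|---|
| 0.90 | 661 | below 50% | 391 | 17.9% | 9.3 |
| 0.85 | 644 | 54% | 381 | 35.3% | 18.6 |
| 0.80 | 627 | 80% | 370 | 57.1% | 22.4 |
| 0.75 | 609 | 94% | 360 | 77.3% | 16.8 |
| 0.70 | 592 | 99% | 350 | 91.0% | 8.0 |
| 0.65 | 575 | >99% | 340 | 97.4% | 2.5 |

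The overstatement of events is 22/13 = 1.69, or 69%. The power loss peaks near RR 0.80. Starting from 13,000 women directly, with exponential event times, gives power within about 0.2 points of these values.

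**Step 4: detectable effect.** Solving the formula for 80% power gives an observed RR of about 0.80 with 22,000 participants and about 0.74 with 13,000. Under the table's 80% compliance, true RR = 1 − (1 − observed RR)/0.8. The full-compliance RR therefore moves from 1 − 0.20/0.8 = 0.75 to 1 − 0.26/0.8 = 0.675.

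**Step 5: could 0.8 be a rate pooled over both sexes?** The printed counts would then stand, but with essentially no events in men the rate in women would have to be 0.8 × 22/13 = 1.35 per 100 person-years. Table 1 puts total invasive cancer at 2.2, and the protocol assumes equal rates in the two sexes. Breast cancer would then be 1.35/2.2 = 62% of all invasive cancer in women.

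**The case against.** Three points can be made for the plan.

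**The rate is not labelled by sex.** Table 1 does not say whose rate 0.8 is, and the documents give no sex-specific breast-cancer rate that would strictly exclude a pooled reading. Taking the rate in women as an assumption, power at RR 0.80 would be 57% at 0.8, 67% at 1.0, 75% at 1.2 and 80% at 1.35 per 100 person-years. This is a fair statement of the uncertainty, but the pooled reading conflicts with the protocol's own equal-rates assumption and needs the 62% share shown above. Nothing in the documents supports it. If the sponsor did intend it, the column would still need to say so and give the rate in women.

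**The column drives no decision.** The sample size rests on major cardiovascular events and total invasive cancer. The text of section 6.0 makes no power claim for breast cancer and notes that power for secondary outcomes depends heavily on event frequency. No alpha, analysis or stopping rule uses this column. All of this stands and limits the importance of the error. It does not defend the column, because event frequency is the input that is wrong.

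**The practical harm is limited.** The SAP treats secondary results as hypothesis generating and repeats power only for total CVD, CVD plus all-cause mortality, and total cancer. It is dated February 4, 2022, after the trial ended on December 31, 2020, so a breast-cancer result will be read mainly from its hazard ratio and confidence interval. This also stands. The remaining risk is that a reader takes the 80% figure at face value when judging a null result.

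**Conclusion.** The concern holds. The column states a power that the design does not have. Expected breast-cancer events are overstated by 69%, and power at an observed RR of 0.80 is about 57% instead of 80%. The largest loss in the tabulated rows is 22.4 points like for like, or 22.9 against the printed, rounded 80%.

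The corrected figures rest on two assumptions: that 0.8 per 100 person-years is the rate in women, as the equal-rates assumption implies, and that 13,000 women are enrolled. The effect is confined to one secondary outcome. The columns for total CVD, CVD plus mortality and total cancer are untouched.

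**What to change.** Recompute the breast-cancer column of Table 1 on 13,000 women and label it as women only. For observed RRs of 0.90 to 0.65, the entries become about 391, 381, 370, 360, 350 and 340 events, with power of below 50% (dash), 35%, 57%, 77%, 91% and 97%.

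Limit assumption (4) to endpoints that occur in both sexes, and add a sentence saying that the breast-cancer comparison has 80% power only for an observed RR of about 0.74 or lower. If 0.8 was meant as a rate pooled over men and women, say so, give the rate in women and its source, and reconcile it with the total-cancer rate of 2.2.

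The cost is one table column, one qualified assumption and one added sentence. Conduct, sample size and analysis do not change.
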